1.2 Scientific Rationale

In summary, our in vitro and in vivo work to date suggests that:

- A genomics approach can serve as an entry point for the unbiased study of glucocorticoid responses in primary human cells and it can uncover specific mechanisms of immune regulation that can be further characterized by functional studies.
- The response to glucocorticoids is highly cell type-dependent. Therefore, information at the level of individual cell types and the study of patients with specific diseases will be necessary to identify the effects of glucocorticoids that are most likely to be responsible for their clinically beneficial effects.

These observations are the basis for the present study. We will analyze the genomic response to in vivo glucocorticoid administration in patients with SLE by serial sampling of individual immune cell populations before and after glucocorticoid administration (Figure 1). This will allow us to study, in a clinically realistic setting, the effects of glucocorticoids at different doses on the immune system of patients with SLE; the level of interindividual variation in glucocorticoid responses at the molecular level; and the differences at baseline and in response to glucocorticoids between cells from patients and those from the previously studied healthy subjects.

[figure not shown]

Figure 1. Study design. Patients with SLE will be enrolled. Each participant will be randomized to one of 2 dose groups and will receive a single IV dose of the glucocorticoid (GC) methylprednisolone. Blood will be sampled serially for purification of hematopoietic cell subsets. Total RNA will be purified from each cell subset and total RNA-seq and small RNA-seq will be performed. The transcriptome-level changes in response to GC for each cell type will serve as the basis for the identification of the key molecular pathways and cellular functions that are affected by GC in each cell type. Important observations will be followed up by functional analyses.

Glucocorticoids remain a mainstay of therapy in a broad range of conditions, despite their well-recognized adverse effects and a large and rapidly growing number of other drugs with

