7.1 Return of Research Results

Any clinically relevant test results will be shared with the participant throughout the study. Unexpected or incidental medical findings unrelated to the study may occur and may require the participant to follow up with an appropriate physician/healthcare provider for standard medical care or follow-up.

The genetic research in this study is not designed or intended to produce data regarding health risks, incurable conditions, or information contradictory to stated biological relationships between individuals. Therefore, it is not expected that the results from these studies will be returned to volunteers. In the rare event of detecting an incidental finding related to a participant's health, we will share the information with the participant. Genetic counseling and advice is available from the NIH to help participants understand the implications of incidental findings, if necessary.

Table 2. Blood Volumes and Research Uses

Visit	Blood sample	Initial processing	Downstream use
Screening visit	Baseline whole blood sample (116 mL) ^a	60 mL: ^b Isolation of hematopoietic cell sub-types (eg, neutrophils, B cells, CD4+ T cells, CD8+ T cells, monocytes, NK cells)	RNA-level, DNA-level, protein-level, and/or functional assays
		10 mL: PBMC isolation	PBMC banking
		8 mL: Plasma purification	Plasma banking
		8 mL: Hepatitis A, B and C	N/A
		6 mL: HIV	N/A
		5 mL: DNA purification	Genome-wide genotyping and/or DNA sequencing
		4 mL: Acute care panel, C3 and C4 complement levels, calcium, CPK, hsCRP, LFTs, lipid panel, magnesium, random morning serum cortisol, serum pregnancy test	N/A
		4 mL: Anti-dsDNA	N/A
		4 mL: IGRA	N/A
		3 mL: PT/PTT	NA
		3 mL: CBC/diff	N/A
		1 mL: ESR	N/A
Infusion visit	Pre-infusion whole blood sample (90 mL)	60 mL: Isolation of hematopoietic cell sub-types (eg, neutrophils, B cells, CD4+ T cells, CD8+ T cells, monocytes, NK cells)	RNA-level, DNA-level, protein-level, and/or functional assays
		10 mL: PBMC isolation	PBMC banking
		8 mL: Plasma purification	Plasma banking
		5 mL: Serum	Glucocorticoid panel
		4 mL: Acute care panel, serum pregnancy test, C3 and C4 complement levels ^c	N/A
		4 mL: Anti-dsDNA ^c	N/A
		3 mL: CBC/diff	N/A
	Serial post-infusion whole blood samples (90 mL × 2)	60 mL: Isolation of hematopoietic cell sub-types (eg, neutrophils, B cells, CD4+ T cells, CD8+ T cells, monocytes, NK cells)	RNA-level, DNA-level, protein-level, and/or functional assays
		10 mL: PBMC isolation	PBMC banking

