A separate analysis will compare data obtained at the same time point (2 hours or 4 hours) between the high-dose and low-dose groups, to test whether there are significant differences in the transcriptional effect of glucocorticoids at the two doses. Finally, we will identify differences and similarities between the baseline transcriptome and the transcriptional response to glucocorticoids in patients with SLE recruited in this study and in healthy volunteers recruited in our previous study. Since the healthy and the SLE participants come from two different studies, they are not directly comparable in many aspects. Therefore, these results will be derived from the two studies separately and no formal comparison will be made across the two studies. We will present the baseline distribution of gene expression, the distribution of gene expression changes, and the subset of differentially expressed genes. For each cell type, we will generate a list of protein-coding or non-coding transcripts that are shared and a list of transcripts that are different between SLE patients and healthy controls.

Sequencing library preparation and sequencing batches will be carefully designed such that samples from the same participant and cell type are run in the same batch and samples from different participants are evenly distributed across batches. This will keep batch effects to a minimum in the identification of differentially expressed genes. For analyses across different participants, such as comparisons among different cell types, linear regression will be adopted with batch as a regression variable to adjust for batch difference. While prior experience suggests that library preparation is the greatest source of batch-to-batch variation in RNA-seq experiments, if the source of batch effects is unclear or cannot be adequately modeled, then the R package SVA will be used.

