15.6 Adaptive Sample Size Determination

Given the high-throughput data generation strategy of next-generation sequencing, the use of different starting materials for sequencing (mRNA, small RNA, DNA), and the use of serial sampling, standard sample size calculation methods are not appropriate in this case and an adaptive study design is a more realistic approach. Sample size consideration will be based primarily on the power to identify differentially expressed genes. The primary endpoint of the study is a list of human protein-coding genes and non-coding RNAs that are differentially expressed in response to glucocorticoids in patients with SLE, for each of the studied cell types and doses. With a sample size of 20 in each dose group, there would be 90% power to detect a change of effect size 0.72 before and after glucocorticoid by the standard paired t-test. That means, within each dose arm and for each cell type, we could detect a differentially expressed gene with 90% power if the gene expression difference before and after glucocorticoid was no less than 0.72 SD.

Due to the specific properties of RNA-seq data, an advanced mixed-effects negative binomial modeling approach will be adopted for evaluating gene expression change and the significance of the change. This will be achieved with the R package DESeq2, a widely adopted tool for differential expression analysis on sequencing data, which targets the issue of large number of genes and small number of samples. In DESeq2, data from all genes are shared and utilized in assessing the differential expression of each gene. This leads to more stable estimation of differential expression and its variability, and consequently to better power for detecting differentially expressed genes.

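### Cell-type comparisons are within participant, but Section 15.3 treats them as between participants with batch as the only named covariate, and its batch rule does not rule out one cell type per batch

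*Combined protocol and SAP*

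**What the plan says.** Section 15.3 gives the model for comparisons between cell types: "For analyses across different participants, such as comparisons among different cell types, linear regression will be adopted with batch as a regression variable". No other term is named for that regression.

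The same section sets the batch layout: "samples from the same participant and cell type are run in the same batch and samples from different participants are evenly distributed across batches". The fallback is that "if the source of batch effects is unclear or cannot be adequately modeled, then the R package SVA will be used".

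On the source of the samples, the caption of Figure 1 in Section 1.2 states "Blood will be sampled serially for purification of hematopoietic cell subsets". Table 2 (Section 7.1) sets aside 60 mL of each draw (screening, pre-infusion and each post-infusion sample) for "Isolation of hematopoietic cell sub-types (eg, neutrophils, B cells, CD4+ T cells, CD8+ T cells, monocytes, NK cells").

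Two other parts of the plan bear on this. Section 15.3 derives differentially expressed genes separately for each cell type from before/after contrasts, and then contrasts the resulting lists across cell types. Section 15.6 says that "an advanced mixed-effects negative binomial modeling approach will be adopted for evaluating gene expression change".

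**The concern.** If one blood draw is split into several cell types, two cell types from the same person share that person's genetics, disease activity, medication and drug exposure. A comparison between them is paired. Section 15.3 gives it as an example of an analysis across different participants and adjusts for batch only. Left that way, variation between participants stays in the error term of a contrast from which it should cancel.

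The layout rule raises a second question. The unit kept together is one participant's samples of one cell type. Nothing says that a participant's different cell types share a batch, or that every batch contains every cell type. If batch coincided with cell type, the stated adjustment would have nothing to work with.

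Cell-type-dependent response is one of the two knowledge gaps that Section 1.1 names. The regression in Section 15.3 is the only model written down for a direct comparison between cell types. Library and sequencing layout also cannot be repaired once the runs are done.

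**Working it through.** **Reference figure.** The plan gives no figure for cell-type comparisons. The nearest is in Section 15.6: 90% power with n = 20 for a before/after change of 0.72 SD. By two-sided normal approximation, 0.72 × √20 = 3.22, 3.22 − 1.96 = 1.26, and Φ(1.26) = 89.6%, so it reproduces. (The exact paired t-test gives 86.3%; that is a separate matter.) The values n = 20, 0.72 and nominal two-sided 0.05 are carried forward for illustration.

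**Step 1: one sample per participant and cell type.** Let σ be the SD of a single sample and ρ the correlation between two cell types of the same participant. The documents give no ρ, so 0.3, 0.5 and 0.7 are assumptions.

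- SE with participant omitted: σ√(2/n)
- True SE: σ√(2(1 − ρ)/n)
- Ratio: 1/√(1 − ρ)
- True type I error of the unpaired test: 2[1 − Φ(1.96/√(1 − ρ))]
- Power, unpaired: Φ([0.72/√(2/20) − 1.96]/√(1 − ρ)), where 0.72/√(2/20) = 2.277
- Power, paired: Φ(0.72/√(2(1 − ρ)/20) − 1.96)

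| Assumed ρ | SE ratio | True type I error | Power, unpaired | Power, paired |
|---|---|---|---|---|
| 0.3 | 1.20 | 0.019 | 65% | 78% |
| 0.5 | 1.41 | 0.0056 | 67% | 90% |
| 0.7 | 1.83 | 0.0003 | 72% | 99% |

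Here 0.72 is in single-sample SD units. At ρ = 0.5 the SD of a paired difference is √(2 × 0.5) = 1, so the paired figure equals the reference figure. These are per-gene values before any multiplicity adjustment.

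**Step 2: time points pooled as independent.** Two cell types, 20 participants and three time points were simulated (20,000 runs) under no cell-type difference. The variance shares are assumed.

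| Participant | Participant × cell type | Residual | Type I error, unpaired and pooled |
|---|---|---|---|
| 0.5 | 0 | 0.5 | 0.008 |
| 0.5 | 0.25 | 0.25 | 0.055 |
| 0.3 | 0.3 | 0.4 | 0.090 |
| 0.2 | 0.5 | 0.3 | 0.150 |
| 0 | 0.5 | 0.5 | 0.169 |

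A paired test on participant means stayed between 0.049 and 0.052 throughout. The direction of the error therefore depends on how much participant-by-cell-type variance there is.

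**Step 3: the batch rule.** Suppose all B-cell libraries go in one batch and all monocyte libraries in another. Each participant-and-cell-type set stays together, and every participant appears once in each batch, so both stated conditions are met. The design matrix (intercept, cell type, batch) then has rank 2 of 3, and the cell-type contrast in expression level cannot be estimated. SVA cannot help, because the data hold nothing that distinguishes the two. A before/after change within a cell type is unaffected, since both of its samples sit in one batch.

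**Step 4: dose.** Forty participants (20 + 20) were allotted to batches at random, without regard to dose, and batch was adjusted for (50,000 runs; batch sizes assumed).

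| Batches × participants | Mean efficiency of the dose contrast | Chance that some batch holds one dose only |
|---|---|---|
| 2 × 20 | 97% | 0% |
| 4 × 10 | 92% | 0.2% |
| 5 × 8 | 90% | 1.6% |
| 8 × 5 | 82% | 31% |

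**The case against.** The strongest reply is that little of the study's output depends on this regression. The primary endpoint is a gene list for each cell type and dose. Those lists, and the cell-type-specific genes read from them in Section 15.3, come from before/after contrasts that the batch rule keeps within one batch. No primary or secondary endpoint is a formal contrast between cell types. This stands. A reader might infer that the cell-type-specific gene lists are compromised; the documents do not support that.

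It can also be said that the standard errors are not shown to be wrong: batch is called a regression variable, not the only one, and Section 15.6 announces a mixed-effects model. The first half stands, so the error is conditional on fitting the model as written. The second does not close the gap. The phrase in Section 15.6 concerns expression change before and after glucocorticoid, writes out no participant term, and describes a different model from the linear regression in Section 15.3.

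A reader might infer that confounded batches are planned. They are not. Section 15.3 promises careful batch design, and adjusting cell-type comparisons for batch makes sense only if batches hold more than one cell type. The rule is incomplete rather than confounded by intent.

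A reader might also infer that dose is confounded with batch. Dose is randomised evenly, participants are spread evenly over batches, and batch is a covariate in cross-participant analyses. What remains is a precision loss that is modest unless batches are small.

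Finally, Table 2 does not prove that every participant yields RNA-seq data for every cell type at every time point. Its list is by example, and the downstream assays are optional alternatives. Pairing may be incomplete, but the cell types still come from the same people.

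**Conclusion.** The point holds as a gap in a stated secondary method. Section 15.3 places a within-participant comparison among the between-participant ones and names no participant term. With one sample per participant and cell type, the consequence is conservative: at an assumed ρ of 0.5 the SE is 1.41 times too large, and power for a 0.72 SD difference with n = 20 falls from 90% to 67%. With pooled time points the test may be conservative or may reject too often (0.008 to 0.169 against a nominal 0.05 in the settings tried). The correlations and variance shares are assumptions, so these figures show direction and rough scale rather than predict this trial.

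Complete aliasing of cell type with batch is permitted by the wording but not planned. The primary before/after lists and their contrast across cell types are untouched. For dose, the matter is one of precision, not bias.

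**What to change.** In Section 15.3:

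1. Describe comparisons among cell types as within participant.
2. Fit cell type (by time where relevant) with participant as a block or random effect. Add a participant-by-cell-type term if time points are pooled. Keep batch where it is estimable.
3. State that all of a participant's cell types and time points share a batch, or that each batch holds all cell types.
4. Spread the two dose groups over batches as evenly as is practical. This is a minor gain in precision, not a correction of confounding.

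The cost is SAP wording and a fixed laboratory layout, with some library preparation waiting until a participant's set is complete. Strict dose balance in every batch would also make libraries wait for participants from the other arm during a 48-month accrual period, which is why item 4 asks only for practical evenness. Items 3 and 4 need settling before libraries are prepared; item 2 can be written at any time before analysis.

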15.4 Analysis of Flow Cytometry and Cytokine Data

Visualization and gating for the flow cytometry data will be performed with the software program FlowJo.

Analysis of flow cytometry and high-throughput cytokine measurement data will be performed in R using custom scripts.

15.5 Summary Statistics for Demographic and Clinical Data

Demographic characteristics and medical history will be summarized, eg, proportion, mean, median, standard deviation, and minimum and maximum values. Means and standard deviations will be reported for all continuous variables; percent will be reported for categorical variables.

15.6 Adaptive Sample Size Determination

Given the high-throughput data generation strategy of next-generation sequencing, the use of different starting materials for sequencing (mRNA, small RNA, DNA), and the use of serial sampling, standard sample size calculation methods are not appropriate in this case and an adaptive study design is a more realistic approach. Sample size consideration will be based primarily on the power to identify differentially expressed genes. The primary endpoint of the study is a list of human protein-coding genes and non-coding RNAs that are differentially expressed in response to glucocorticoids in patients with SLE, for each of the studied cell types and doses. With a sample size of 20 in each dose group, there would be 90% power to detect a change of effect size 0.72 before and after glucocorticoid by the standard paired t-test. That means, within each dose arm and for each cell type, we could detect a differentially expressed gene with 90% power if the gene expression difference before and after glucocorticoid was no less than 0.72 SD.

Due to the specific properties of RNA-seq data, an advanced mixed-effects negative binomial modeling approach will be adopted for evaluating gene expression change and the significance of the change. This will be achieved with the R package DESeq2, a widely adopted tool for differential expression analysis on sequencing data, which targets the issue of large number of genes and small number of samples. In DESeq2, data from all genes are shared and utilized in assessing the differential expression of each gene. This leads to more stable estimation of differential expression and its variability, and consequently to better power for detecting differentially expressed genes.

Based on the data from our previous study of healthy volunteers (protocol 16-I-0126) and a bootstrap procedure, with a sample size of 20 we can detect differentially expressed genes from 0 to 2 hours after glucocorticoid infusion with a median of 0.45 log₂ fold change at a significance level of 0.05 after adjusting for multiplicity, and 0.62 log₂ fold change from 0 to 4 hours. In SLE patients, there may be higher variability in the data than what we observed in healthy volunteers. Meanwhile, the magnitude of gene expression changes is also expected to be higher, given the state of activation of many immune cells in SLE compared to healthy controls. Therefore, we estimate that the proposed initial sample size in this study will be sufficient to detect the genes associated with the effect of glucocorticoids in SLE patients.

To empirically evaluate whether this estimate is correct, we propose an adaptive study design similar to the one we performed on the study with healthy volunteers. Specifically, we will

recruit an initial cohort of 20 participants in each dose group. Based on the observed data from 20 participants, we will then assess the gain in discovery with up to 30 additional participants per group. We will perform a bootstrap procedure, sampling with replacement up to 50 units from the 20 observed participants in each group to evaluate the improvement in gene detection. For example, if the subset of genes that can be detected as differentially expressed over time and the subset of genes that can be detected as differentially expressed over the 2 doses do not change significantly above a number, then we will stop at that number. If there is change in the gene subsets, but the pathways and the biological interpretation of the data remain unchanged, then additional participants will be unlikely to change the outcome of the study and no further recruitment will be pursued. Due to the adaptive sample size determination, we will again use a nominal significance level $\alpha < 0.05$.

16 Ethics/Protection of Human Subjects

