The glucocorticoid dosing regimens that are administered to patients with SLE in current clinical practice are arbitrary and not based on detailed knowledge of the effects of glucocorticoids at different doses on cells of the immune system. This unfortunately means that there may be unnecessary harm in current clinical practice. While repeated exposure to very high doses of glucocorticoids can lead to debilitating side effects, the extent to which such doses have effects on cells of the immune system that differ substantially from those achieved with lower doses remains unclear. Because the level of disease activity in patients with SLE tends to fluctuate over time, and higher doses are generally used to treat patients with higher disease activity, this patient population is particularly susceptible to the potential harm of arbitrary glucocorticoid dosing regimens. Therefore, a secondary aim of this study is to analyze the transcriptional response to in vivo administration of glucocorticoids at a range of clinically used doses.

Glucocorticoids act primarily by binding in the cytosol to the glucocorticoid receptor (GR), a nuclear receptor of the steroid/thyroid hormone receptor superfamily.³ The ligand-bound GR translocates into the nucleus and can directly bind DNA at specific recognition sequences known as glucocorticoid response elements (GREs), increasing or decreasing transcription rates depending on the type of GRE.^{4,5} In addition, ligand-bound GR can be recruited to specific genomic sites without directly binding DNA, via protein-protein interactions with other

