15.3 Identification of Glucocorticoid-responsive Genes

To identify glucocorticoid-responsive genes, differential expression analysis for the RNA-seq and small-RNA-seq data will be performed in R, with the package DESeq2.⁴⁶

For each cell type, we will assess the level of variation in the baseline measurements by comparing the expression values on the day of the screening visit to the 0-hour (pre-infusion) values on the day of the glucocorticoid infusion. For participants who undergo a glucocorticoid taper, this analysis will contrast the pre- and post-taper patterns of gene expression. We will then perform differential analysis comparing each of the two post-infusion time points (2 hours and 4 hours) independently against the baseline. DESeq2 (section 15.6) adopts the method of Benjamini-Hochberg to adjust for multiplicity. We will draw conclusions based on the Benjamini-Hochberg adjusted p values, which control for the family-wise false discovery rate (FDR) in the presence of multiple comparisons. We will employ a cutoff FDR⁴⁷ value of < 5% to

select the transcripts that will be considered differentially expressed in each cell type at each time point. The resulting gene lists will be contrasted to determine, for example, which genes are uniquely differentially expressed in a specific cell type, or common to a specific hematopoietic lineage. They will also be used for pathway enrichment analysis, to determine the molecular pathways and biological functions that are most responsive to the glucocorticoid stimulus in each cell type.

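### The 90% power at 0.72 SD in section 15.6 is 86.3% by the paired t-test it names (two-sided 0.05, SD of change), and it is not power under the plan's FDR < 5% rule

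*Combined protocol and SAP*

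**What the plan says.** Section 15.6 bases the sample size primarily on power to identify differentially expressed genes. It gives one numeric power: "With a sample size of 20 in each dose group, there would be 90% power to detect a change of effect size 0.72", by the standard paired t-test. It then explains that, within a dose arm and cell type, "we could detect a differentially expressed gene with 90% power if the gene expression difference" before and after glucocorticoid is at least 0.72 SD. Alpha, sidedness and the SD used are not stated beside the figure.

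The same section says that DESeq2 will be the actual analysis and that sharing data across genes leads to more stable estimates, "and consequently to better power for detecting differentially expressed genes". No power figure is given for DESeq2.

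Section 15.3 defines the event: "We will draw conclusions based on the Benjamini-Hochberg adjusted p values", with an FDR cutoff below 5% used to "select the transcripts that will be considered differentially expressed in each cell type at each time point".

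Section 15.6 also reports a bootstrap on the healthy-volunteer study. With 20 participants the median detectable change is 0.45 log2 fold from 0 to 2 hours and 0.62 from 0 to 4 hours, "at a significance level of 0.05 after adjusting for multiplicity". No power is attached to these values.

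**The concern.** The 90% is the only numeric power offered for the primary endpoint, which is the list of differentially expressed transcripts for each cell type and dose. A reader will take it as the chance that a gene with a 0.72 SD change enters that list.

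There are two separate reasons to doubt that reading. The named test does not appear to give 90% at 0.72 SD with 20 pairs. In addition, the figure describes one unadjusted test, whereas entry to the list requires passing a Benjamini-Hochberg cutoff across all transcripts tested. If both doubts hold, the plan overstates how sensitive the list is, and the absence of a gene from it would be read as stronger evidence of no response than it is.

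**Working it through.** **Inputs.** From section 15.6: n = 20 pairs per dose group, effect size d = 0.72, paired t-test (19 degrees of freedom), stated power 90%. From section 15.3: Benjamini-Hochberg FDR < 5%. Section 12.9 replaces participants who leave before infusion, so n = 20 is used without inflation.

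**Assumptions.** Alpha is 0.05. The test is two-sided, because section 1.1 describes glucocorticoid action as "increasing or decreasing transcription rates depending on the type of GRE". The SD is that of the within-participant change, the usual paired effect size.

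**Step 1: reproduce the stated figure.** The normal approximation is power = Φ(d√n − 1.960). Here d√n = 0.72 × √20 = 3.220, so power = Φ(1.260) = 89.6%. Inverting for 90%, d = (1.960 + 1.282)/√20 = 0.725. The stated pair is therefore a normal-approximation result.

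**Step 2: the test the plan names.** The exact power uses a noncentral t with 19 degrees of freedom, noncentrality 3.220 and critical value 2.093:
- Power at 0.72 SD is 86.3%. A simulation of 400,000 draws gives the same.
- 90% at n = 20 needs d = 0.764.
- 90% at d = 0.72 needs n = 23 (91.0%); n = 22 gives 89.6%.
- 90% at d = 0.72 and n = 20 would need a two-sided alpha of 0.072.
- One-sided 0.05 gives 92.7%, with 90% at 0.679 SD, so it does not recover 0.72 either.

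**Step 3: the other reading of SD.** If 0.72 is in units of a single measurement's SD, then d for the change is 0.72/√(2(1 − ρ)), where ρ is the before/after correlation. The documents do not give ρ. Exact two-sided power is 58.0% at ρ = 0, 73.3% at 0.30, 86.3% at 0.50, 90.0% at 0.556, 92.7% at 0.60 and 97.6% at 0.70.

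**Step 4: power under the FDR rule.** If k of m tested transcripts are declared, the Benjamini-Hochberg cutoff on the raw p value is 0.05 × k/m. It cannot exceed 0.05 and reaches 0.05 only when all are declared. The effect sizes of the other transcripts matter only through k/m. The share k/m is not given for SLE, so a range is shown. These are two-sided paired t-test values with n = 20, not DESeq2 values.

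| Share declared | Raw-p cutoff | Power, 0.72 SD of change | Power if the unadjusted figure really were 90% (d = 0.7645) |
|---|---|---|---|
| 100% | 0.05 | 86.3% | 90.0% |
| 50% | 0.025 | 77.7% | 82.8% |
| 20% | 0.01 | 64.1% | 70.6% |
| 10% | 0.005 | 53.2% | 60.2% |
| 2% | 0.001 | 30.3% | 36.4% |

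**Check on Step 4.** The cutoff rule was tested by simulation (20,000 independent genes, 30 repeats, responders split equally between 0.72 and 1.5 SD). With 10% responders, the share declared was 0.078 and power at 0.72 SD was 0.497, against 0.494 predicted. With 30% responders, the share was 0.261 and power 0.682, against 0.683.

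**The case against.** The arithmetic gap is small: 3.7 points, or 0.72 against 0.764 SD. It is the familiar difference between the normal approximation and the t distribution. The 86.3% also depends on inputs that section 15.6 leaves out. This stands: 86.3% is a ceiling only for a two-sided 0.05 t-test with the SD of change. It does not rescue the text, which names a t-test and leaves the reader to guess the rest.

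A high before/after correlation could make the plan's claim true even under the FDR rule. If 0.72 refers to a single measurement's SD and ρ is 0.75, power is 94.2% with 20% of transcripts declared and 89.7% with 10%. This is arithmetically right. But the unadjusted power would then be about 99%, so the stated 90% would be wrong in the other direction. Wherever the unadjusted figure is exactly 90%, power under the rule is 90% only if every transcript is declared.

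The lowest values in the table rest on an assumed share and on a t-test standing in for DESeq2. That is so, and no ceiling for DESeq2 has been shown. However, the plan's 90% is itself a t-test figure, and the DESeq2 results will be Benjamini-Hochberg adjusted too.

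Section 15.6 also says standard sample size methods do not suit this study. It adds a multiplicity-adjusted bootstrap and allows up to 30 more participants per group. These support the sample size independently of the t-test, so the enrolment number is not undermined. They attach no power to any effect, so the 90% stays uncorrected.

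**Conclusion.** The concern holds. For a two-sided 0.05 paired t-test with 0.72 in SDs of the within-participant change, power with 20 per group is 86.3%, not 90%. This part is small and depends on those assumptions.

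The more important part does not depend on how alpha, sidedness or the SD are resolved. A single-test power has been described as power to detect a differentially expressed gene, an event that section 15.3 makes harder to reach. Power under that rule is below the single-test value unless every tested transcript is declared. How far below depends on the share declared, which the documents do not give for SLE: for the t-test at 0.72 SD of change, from 77.7% at a 50% share down to 30.3% at 2%.

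The stated power should be corrected. Neither the initial 20 per group nor the adaptive step has been shown to be wrong.

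**What to change.** In section 15.6, restate the figure with its alpha, sidedness and SD. For example: for a single transcript at unadjusted two-sided alpha 0.05, a paired t-test with 20 per dose group has 86% power at a change of 0.72 SD of the within-participant change, and 90% at 0.76 SD. If a single measurement's SD was meant, say so, give the assumed before/after correlation, and recompute the power from it.

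Delete the sentence that equates this with 90% power to detect a differentially expressed gene. State instead that transcripts are declared at Benjamini-Hochberg FDR < 5% as in section 15.3, and that power under that rule is lower than the single-test figure.

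If the healthy-volunteer bootstrap can supply it, add a DESeq2 power under the FDR rule. Section 1.3 says that study used 250 mg, so the result would not cover the 1 mg/kg arm or SLE variability and should be labelled accordingly. The main correction does not depend on this addition.

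The cost is rewording, plus the optional bootstrap summary. The stated power becomes less favourable; enrolment and the adaptive rule do not change.
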